AIM 3: To examine the feasibility, fidelity, adherence, acceptability (e.g., perceived barriers to use), and safety (e.g., feeding adequacy) of the opaque, weighted bottle intervention. We will collect both objective and subjective data related to bottle use. We will also assess mothers' perceptions of the opaque bottles, any perceived barriers to their use, and whether baseline characteristics of mothers (e.g., weight status, race/ethnicity, socioeconomic status, parity, other non-maternal caregiver feeding practices and styles) and infants (e.g., sex, weight status, temperament) moderate intervention effects.

The proposed study is a critical step toward understanding the potential for opaque, weighted bottles as a practical solution for reducing obesity risk during infancy. Additionally, given the demographics of our community (35% Hispanic; 34% minority races), we have the opportunity to test this intervention in a diverse sample that includes a large proportion of families of lower socioeconomic status, two major risk factors for unhealthy bottle-feeding practices and childhood obesity.

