#### **METHODS:**

#### **Design and Sample**

Design. We have designed a 12-week randomized clinical trial to explore the efficacy

and feasibility of a 12-week opaque, weighted bottle intervention. Previous research suggests that, during early infancy, 12 weeks is a sufficient duration of follow-up to capture divergences in growth trajectories related to feeding mode, and that the window between 12-24 weeks is when associations between feeding mode and excess weight gain emerge. Mother-infant dyads will be randomized to use conventional, clear bottles (*clear* group) or opaque, weighted bottles (*opaque* group). Dyads will participate in home-based assessments of bottle-feeding interactions at study entry and 12 weeks, with brief assessments at 2 and 6 weeks.

**Subjects and Recruitment.** A total of 100 mother-infant dyads will participate. We will use recruitment methods similar to those effectively used in our previous research. Mothers will be recruited through ads in local newspapers; targeted social media ads; Women, Infant & Children (WIC) offices; OB/GYN and pediatrician offices; mass mailings; online sites; and a list of past participants who have asked to be notified of future studies. See **Appendix 1** for example recruitment materials.

Given San Luis Obispo and Santa Barbara Counties are predominately White and Hispanic (66% White, 35% Hispanic, 2% Black, and 4% Asian), we will over-sample Black mothers to increase sample diversity (targets: 55% White, 35% Hispanic, 13% Black, 4% Asian). Both English and Spanish-speaking mothers and their healthy, term infants of either sex will be eligible.

Inclusion criteria for the dyads include:

- 1) mothers 18-40-years of age
- 2) infants <8-weeks of age
- 3) mother is planning to bottle-feed, or is currently bottle-feeding, her infant
- 4) mother predominantly or solely responsible for infant feeding
- 5) dyad has a pediatrician and plans to attend infant well-visits
- 6) mother is willing to use stainless-steel bottles and to provide the study will her current bottles, which would be returned after study completion
- 7) prior to the introduction of solid foods

To protect infants who might be at risk for underfeeding or inadequate growth, exclusion criteria for infants include known risk factors:

- 1) preterm birth (i.e., gestational age <37 weeks)
- 2) low birth weight (<2500 g)
- 3) maternal smoking during pregnancy

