- Feasibility, Fidelity, Adherence, and Acceptability will be assessed through a number of objective and subjective measures (see Appendix 5). Feasibility of recruitment and retention will be evaluated by: (a) tracking the number of women who respond to advertisements, are eligible, but decline participation; (b) examining whether recruitment targets are met across different ethnic/racial strata; (c) assessing the number of participants who agree to participate but drop out or are lost to followup, and determining reasons for drop out. To assess feasibility and fidelity of treatment conditions, interventionists will track distribution of the informational brochure (in each group) and brief phone calls completed. We will ask participants about any crossbottle usage (e.g., the *clear* group using opaque bottles or *vice versa*). Adherence will be assessed by mothers' self-reports of the extent to which they used their assigned bottles (i.e., estimated percentage of feedings) at the 2-, 6-, and 12-week assessments. During these assessments, we will also assess whether infants experienced any illnesses that might have interfered with their typical feeding behaviors or weight gain, or whether mothers changed bottles, nipples, or formulas. We will also objectively measure bottle-usage and feeding patterns by affixing a light-weight, proprietary intake-tracking device to the bottoms of the bottles of all mothers within both the control and intervention groups. We developed this device to allow for objective and unobtrusive tracking of infants' intake in free-living settings; the device tracks infant feeding patterns by assessing the weight of the bottle before and after each feeding and time stamping each feed start and end. The device is dishwasher safe and has the capacity to store 6-months of feeding data, thus can be used for the entire duration of the proposed study. Although this device is still under development, preliminary tests have shown it is highly valid, with measurement error <0.05 oz. Acceptability will be

assessed by querying mothers about their perceptions of their bottles and any barriers to use of the bottles.

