#### **Statistical Considerations**

Data Analysis. All quantitative analyses will be conducted using SAS v.9.4 (SAS Institute Inc., North Carolina, USA). Oualitative interview data will be transcribed and sorted into thematic categories using constant comparison within the framework of grounded theory. We will use linear regression to model the change in infant intake and maternal responsiveness (Aim 1) and change in WLZ, skinfolds, waist circumference (Aim 2) by the primary study variable of *clear* versus *opaque* group. For Aim 3, we will examine the feasibility, fidelity, adherence, acceptability, and safety of the intervention by summarizing quantitative and qualitative data related to recruitment and retention, mothers' use of their assigned bottles, perceptions of and barriers to using the bottles, and any issues related to infant inadequate weight gain or weight loss. We will then explore whether variations in intervention feasibility, fidelity, adherence, acceptability or safety are correlated with baseline characteristics of mothers (e.g., weight status, race/ethnicity, socioeconomic status, parity, feeding practices and styles, non-maternal caregiver involvement in feeding) and infants (e.g., sex, birth weight, weight status, temperament). Finally, we will assess whether the effects of the intervention on infant intake, maternal responsiveness, and infant WLZ change are moderated by the following factors: nipple type; mothers' adherence to the intervention, race/ethnicity, parity, or feeding practices and styles; infants' sex, temperament, and timing of solid food introduction; and the extent to which non-maternal caregivers are feeding the infant. Moderation will be explored by including a group by moderator interaction term in the linear regression models used to explore Aims 1 and 2. All inferential analyses will be preceded by appropriate descriptive statistics and graphs to determine that assumptions for linear regression are satisfied.

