#### Potential Risks and Plan for Data Safety and Monitoring

**Potential Risks.** The risk involved in this study is considered minimal. Some infants or mothers may dislike using the bottles we offer during the infant-feeding study, thus may perceive the experience of using these bottles as unpleasant. It is also possible that an unintended consequence of the opaque bottles will be that mothers and caregivers underfeed their infants, resulting in inadequate growth for their infants. Some mothers may feel uncomfortable answering questions about their attitudes about and concern for their infants' feeding and weight gain patterns. Additionally, some dyads may experience discomfort related to having their feedings video-recorded or having our research staff present in their homes. There is also risk of breach of confidentiality given that video records are being collected.

**Plan for Data Safety and Monitoring.** We have developed effective procedures for protecting participants' safety and confidentiality. All participants will be assured that they have the right to opt out of any part of the study with which they feel uncomfortable. Additionally, we will check-in with mothers and infants frequently to monitor infants for insufficient growth (<20-30g/day) or weight loss. The research assistants will monitor the participants for adverse events, including inadequate infant growth.

The PI will hold primary responsibility for ensuring that the proposed trial is conducted according to protocol and carrying out the above data safety and monitoring plan. However, the PI will also identify a local pediatrician to serve as the Data and Safety Monitor (DSM) for the proposed study. Given that feeding interactions and infant growth are of primary interest, we will identify a local pediatrician with particular expertise in this area and have several pediatricians affiliated with our research center who have this expertise. Once appointed, the DSM will help ensure that our protocol and intervention and assessment of adverse events are in line with local pediatric providers' usual care plans. The DSM will meet with the PI and Co-I's quarterly to review and evaluate the accumulated study data for participant safety, study conduct and progress, and alignment with pediatric providers' usual care plans. The DSM will also ensure that all enrolled families have a pediatrician with whom they regularly consult to add an additional layer of monitoring and protection.

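### The group-by-adherence interaction compares opaque use in one arm with clear use in the other, so it cannot show moderation; timing of solid foods is a weaker case of the same problem

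*Combined protocol and SAP*

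**What the plan says.** Statistical Considerations, Data Analysis, plans to assess whether effects on infant intake, maternal responsiveness and WLZ change are moderated by a list that includes nipple type, "mothers' adherence to the intervention, race/ethnicity, parity, or feeding practices and styles; infants' sex, temperament, and timing of solid food introduction", and non-maternal feeding. The method is given in one sentence: "Moderation will be explored by including a group by moderator interaction term in the linear regression models used to explore Aims 1 and 2". Shortly before, the same paragraph treats adherence as a result, to be correlated with baseline characteristics.

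Aim 3, in the Statement of Purpose, frames moderation as "whether baseline characteristics of mothers (e.g., weight status, race/ethnicity, socioeconomic status, parity, other non-maternal caregiver feeding practices and styles", with a parallel list for infants.

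Under Measures (Feasibility, Fidelity, Adherence, and Acceptability): "Adherence will be assessed by mothers' self-reports of the extent to which they used their assigned bottles", as an estimated percentage of feedings at the 2-, 6- and 12-week assessments. An intake-tracking device on the bottles of both groups is also to record bottle use. The Randomization paragraph says mothers learn their group at the end of Pre-Test 2, in study week 1.

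On solids, the inclusion criteria require entry "prior to the introduction of solid foods". The section on additional potential moderators collects whether and when solids begin, by retrospective maternal report.

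**The concern.** A moderator analysis asks whether the effect of allocation differs between kinds of dyad that exist before allocation. Adherence fails that in two ways.

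First, it is observed after allocation and may be shaped by it. Second, it does not measure the same thing in the two arms. A value of 90% means 90% opaque feeds in one arm and 90% clear feeds in the other. The interaction coefficient is the opaque-arm slope of outcome on opaque use minus the clear-arm slope of outcome on clear use. That difference does not say whether the bottle works better in more adherent mothers, whatever its p-value.

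There is also a plausible route to unequal slopes. Potential Risks says: "It is also possible that an unintended consequence of the opaque bottles will be that mothers and caregivers underfeed their infants". If a mother whose infant gains slowly on opaque bottles stops using them, low adherence goes with low gain in that arm. The opaque-arm slope is then positive, and the interaction could be misread as more use causing more gain. The Measures section says the study should inform the feasibility of scaling up to larger trials, so such a reading could be carried forward.

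Timing of solids is likewise fixed after entry, and it is seen only for infants who start within the 12 weeks.

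**Working it through.** **1. Order of events.** Group is disclosed in study week 1. Adherence is reported at weeks 2, 6 and 12. Entry precedes solids, so every start of solids comes later. Neither variable is a baseline value.

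**2. Inputs from the plan (Power calculations).** n = 100, α = .05, SD of WLZ 1.0, correlation over 12 weeks .45. The allocation ratio and sidedness are not stated; 1:1 (50 per arm) and two-sided are assumed. These inputs reproduce the plan's own figure:

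- SD of change = √[2 × 1.0² × (1 − 0.45)] = 1.049
- Detectable difference = (1.960 + 0.842) × 1.049 × √(2/50) = 0.588, against 0.59 stated

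**3. Inputs that are assumed.** The documents give no adherence spread and no adherence-outcome correlation. Both are varied below. SDs are in percentage points; the outcome is scaled to SD 1, which does not affect the test.

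**4. The planned test.** Change is regressed on group, adherence and group × adherence:

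t = (b_opaque − b_clear) / √[s²(1/S_clear + 1/S_opaque)], df = 100 − 4 = 96

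Here b is the within-arm slope, S the within-arm sum of squares of adherence and s² the pooled residual variance.

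**5. Rejection rates with the bottle effect set to zero.** 40,000 simulated trials per setting, 50 per arm, nominal 5%:

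| Adherence SD, clear / opaque | r = 0.2 in opaque arm only | r = 0.3 | r = 0.4 |
|---|---|---|---|
| 20 / 20 | 16% | 32% | 52% |
| 8 / 20 | 8% | 13% | 19% |
| 5 / 20 | 6% | 9% | 12% |
| Equal slopes in both arms | about 5% | about 5% | about 5% |

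With 48 per arm (120 recruited × 0.80 = 96), rates move by at most about 2 points. The sign of r does not change the rate; a significant result takes the sign of the opaque-arm slope.

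**6. Hand check.** With slope zero in the clear arm, the expected test statistic is roughly

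d = r√n / √[(1 − r²/2)(1 + (SD_opaque/SD_clear)²)]

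For r = 0.3 and n = 50, the numerator is 0.3 × 7.071 = 2.121 and 1 − r²/2 = 0.955.

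- SD 20/20: d = 2.121/√(0.955 × 2) = 1.535, rejection about 34% (simulated 32%)
- SD 8/20: d = 2.121/√(0.955 × 7.25) = 0.806, about 13% (simulated 13%)
- SD 5/20: d = 2.121/√(0.955 × 17) = 0.526, about 8% (simulated 9%)

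**7. Solids.** The inclusion criteria give "infants <8-weeks of age", so infants finish under 8 + 12 = 20 weeks old; the Statement of Purpose says under 2 weeks at entry, hence under 14. Later starts are not observed. Assume 10 / 20 / 30% start by week 12, and starters differ by 0.5 SD in WLZ change in one arm only: rejection is 11 / 16 / 20%. The same difference in both arms gives 5%.

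**The case against.** **The plan breaks its own Aim 3.** A reader might infer this, but the documents do not support it. Aim 3 names baseline characteristics without saying only those, the section on additional potential moderators lists solids, and the analysis paragraph names both factors openly. The list goes beyond the aim's wording; it does not breach a limit.

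**The rejection rates measure the harm.** They do not, because every correlation and spread is assumed. If only opaque-arm mothers have a reason to abandon their bottle, clear-arm adherence probably varies less, and the lower rows of the table are the relevant ones. Underfeeding on opaque bottles would itself be a bottle effect, so it fits awkwardly with a zero-effect simulation. It supports the claim that slopes may differ by arm, not any particular rate.

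**The danger is a false finding that the bottle works if used.** The one mechanism in the documents points the other way, to a positive opaque-arm slope.

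**Solids are equally at fault.** They are not. Nothing in the documents suggests that starters would differ in one arm only, and few infants may have started by then.

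**Recoding adherence as share of opaque feeds would rescue the test.** The plan says only "We will ask participants about any crossbottle usage" and states no percentage; recoding would also leave confounding in place.

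**It is exploratory.** True. This limits the severity, but a label does not make the coefficient a moderation effect.

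**Conclusion.** The point stands for adherence. It rests on two facts in the plan, the timing and the definition of adherence, and not on the simulation. The group-by-adherence term cannot show moderation. Under a zero bottle effect its rejection rate ranges from about 5% (equal slopes) to about 52% (the most extreme opaque-only case tabulated), so the excess runs from almost none to large.

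For timing of solids the point is secondary. It is a post-entry variable, only partly observed by week 12, and inflation would need an arm-specific relation that the documents do not suggest.

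A reader might infer that the Aim 1 and Aim 2 results are compromised. They are not: these are separate exploratory models, and the main group comparisons are unaffected. The change should be made, at modest priority, because it alters what the pilot may conclude about adherence.

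**What to change.** In the Data Analysis paragraph:

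- Restrict group-by-moderator terms to values taken at study entry. State this also for nipple type, feeding style and non-maternal feeding, whose timing as moderators is left open.
- Remove adherence and timing of solids from the interaction list.
- Report both descriptively by arm: adherence from self-report and from the tracking device, and the number of infants started on solids by week 12.
- Label any adherence-outcome analysis that is kept as post-randomisation, non-causal and secondary.

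This is a change of wording. The plan already summarises use of assigned bottles and already collects device data and the introduction of solids. The cost is two exploratory interaction tests.

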to infant cues during bottle-feeding. Indeed, in an NIH-funded, laboratory-based trial (R03-HD080730), we illustrated mothers show significantly greater responsiveness and feed their infants 26% less when using opaque, weighted bottles compared to conventional, clear bottles. While initially conceived as a promising adjunct to a larger obesity prevention approach, our laboratory findings suggest that opaque bottles may be a simple, yet potent, stand-alone tool for improving mothers' abilities to feed responsively and reducing infants' risk for overfeeding and rapid weight gain. In the proposed study, we aim to test this approach outside of the laboratory and enroll 100 new, formula-feeding mothers and infants (< 2 weeks old) into a randomized trial to examine the 12-week effects of using opaque, weighted bottles versus clear bottles for improving bottle-feeding interactions and reducing child obesity risk. We will use preestablished and state-of-the-art procedures to objectively measure infants' intake and mothers' responsiveness to infant cues (i.e., objective assessment of feeding patterns, coding of mother-infant bottle-feeding interactions) within their homes at the beginning and end of the 12-week study period. Intervention feasibility, fidelity, acceptability, and safety will be evaluated. Specific aims of the proposed research are:

AIM 1: To test the hypothesis that mothers who use opaque, weighted bottles for a 12-week intervention period will feed their infants less and be more responsive to their infants' cues compared to mothers who use clear bottles. Intake will be objectively assessed via change in bottle weight before and after feeding observations. Responsiveness to infant cues will be coded from video-records of feeding observations using the Nursing Child Assessment Parent-Child Interaction Feeding Scale.

AIM 2: To test the hypothesis that infants who are fed from opaque, weighted bottles will exhibit slower 12-week weight gain trajectories compared to infants who are fed from clear bottles. Infants' weight, length, skinfolds, and waist circumference will be measured at the beginning and end of the study; weight-forlength z-scores (WLZ) will be calculated using the WHO Growth Standards.

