**Power calculations.** The proposed sample size (n=100) was selected so that there will be adequate power to test for statistical significance for study aims. Because our previous research has shown <10% attrition after 12 weeks, we conservatively estimate 20% of participants will drop out and 120 mother-infant dyads will be recruited to account for this predicted attrition rate. For Aim 1, which examines the impact of bottle type on infant intake and maternal responsiveness, there is 80% power to detect a 19.1 mL difference in intake and 1.32 point difference in change of NCAFS score from baseline to 12-week follow-up between the *clear* and *opaque* groups, using  $\alpha = .05$ . For Aim 2, which examines the impact of bottle type on weight for length z-scores (WLZ), there is 80% power ( $\alpha = .05$ ) to detect a difference of 0.59 in change of WLZ from baseline to 12-week follow-up between the *clear* and *opaque* groups. Given rapid weight gain has been defined as z-score change  $\geq 0.67$  SD, a between-group difference in WLZ change of this magnitude (0.59 SD) would be clinically significant. Power calculations are based on a pilot study for which the between-subject standard deviation for infant intake was 33.7 mL and for the NCAFS scales is 1.91; this calculation also assumes that the mothers assigned to the *clear* group will have a higher correlation in scores between baseline and 12-week follow-up (r = .55), whereas mothers assigned to the *opaque* group will have a lower correlation in scores between baseline and 12-week follow-up (r =.40). The latter calculation assumes the standard deviation for WLZ is 1.0, and that the correlation between WLZs over 12-weeks for infants is  $r = .45^{.60}$ 

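### Recruiting 120 with 20% dropout leaves 96 dyads, not the 100 used for power, and the aims say to enrol 100 rather than 120

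*Combined protocol and SAP*

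**What the plan says.** Three places give a sample size.

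- **Statement of Purpose:** the study will "enroll 100 new, formula-feeding mothers and infants (< 2 weeks old) into a randomized trial".
- **Design and Sample, Subjects and Recruitment:** "A total of 100 mother-infant dyads will participate".
- **Statistical Considerations, Power calculations:** "The proposed sample size (n=100) was selected so that there will be adequate power to test for statistical significance for study aims". The next sentence reports that "our previous research has shown <10% attrition after 12 weeks" and continues: "we conservatively estimate 20% of participants will drop out and 120 mother-infant dyads will be recruited to account for this predicted attrition rate".

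The same paragraph claims 80% power at α = .05 for differences of 19.1 mL in intake, 1.32 points in NCAFS change and 0.59 in WLZ change. Only this paragraph mentions 120. Neither of the other two sections describes its 100 as a number of completers.

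**The concern.** There are two faults.

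1. **The dropout allowance does not do what it says.** The figure of 120 is 100 × 1.20. An allowance for 20% loss divides by 0.80, so 120 does not protect 100.
2. **The number to enrol is given two ways.** The aims tie 100 to enrolment in the randomized trial, while the power paragraph recruits 120. The statement that 100 will participate could mean enrolled or completing, so it does not settle the matter.

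The second fault carries the weight. Staff who work from the aims would stop at 100 and have no allowance for attrition, and the 80% power claims for WLZ and intake would then fail at either dropout rate the plan mentions. Recruitment is also a feasibility outcome under Aim 3, which includes "examining whether recruitment targets are met across different ethnic/racial strata". The targets are percentages and do not change with the total, but the counts do: 35% Hispanic is 35 of 100 or 42 of 120. This is a secondary reason to fix one total.

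**Working it through.** **Inputs, all from Power calculations.** Standard deviation (SD): 33.7 mL for intake, 1.91 for NCAFS, 1.0 for WLZ. Baseline to 12-week correlation: .55 (clear) and .40 (opaque) for intake and NCAFS, .45 for WLZ. α = .05. Two-sided testing and 1:1 allocation are my assumptions. Power is from the noncentral t distribution.

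**Change-score SDs**, from SD × √(2(1 − r)), averaging the variances of the two arms:

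- WLZ: √(2 × 0.55) = 1.049
- Intake: 33.7 × √((0.90 + 1.20)/2) = 33.7 × √1.05 = 34.5 mL
- NCAFS: 1.91 × √1.05 = 1.96

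**Reproducing the plan's figures at 100 analysed (50 per arm).** The difference detectable with 80% power is 0.594 for WLZ (stated 0.59). For intake it is 19.07 mL with the raw SD of 33.7 (stated 19.1), or 19.5 mL with the change-score SD. So 100 is the analysed number behind these two claims. NCAFS does not reproduce: the inputs give about 1.11 points, not 1.32. That is a separate mismatch.

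**Dropout arithmetic.**

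- 120 × 0.80 = 96
- 100/0.80 = 125
- 1 − 100/120 = 16.7%
- 120 × 0.90 = 108
- 100 × 0.80 = 80
- 100 × 0.90 = 90

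**Power at the plan's stated differences.** Intake is shown for the raw SD, then the change-score SD.

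| Scenario | Completers | WLZ 0.59 | Intake 19.1 mL | NCAFS 1.32 |
|---|---|---|---|---|
| Basis of the plan | 100 | 79.5% | 80.1% / 78.2% | 91.6% |
| 120 enrolled, 20% loss | 96 | 77.9% | 78.5% / 76.5% | 90.5% |
| 120 enrolled, 10% loss | 108 | 82.5% | 83.1% / 81.3% | 93.5% |
| 100 enrolled, 20% loss | 80 | 70.0% | 70.7% / 68.5% | 84.6% |
| 100 enrolled, 10% loss | 90 | 75.1% | 75.8% / 73.7% | 88.6% |

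**Cost of each fault.**

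- 96 instead of 100 completers: WLZ 79.5 − 77.9 = 1.6 points; intake 80.1 − 78.5 = 1.6 or 78.2 − 76.5 = 1.7 points.
- 100 instead of 120 enrolled, 20% loss: WLZ 77.9 − 70.0 = 7.9 points; intake 78.5 − 70.7 = 7.8 or 76.5 − 68.5 = 8.0 points.
- 100 instead of 120 enrolled, 10% loss: WLZ 82.5 − 75.1 = 7.4 points; intake 83.1 − 75.8 = 7.3 or 81.3 − 73.7 = 7.6 points.

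**Differences detectable with 80% power at 96 completers:** 0.61 WLZ, and 19.5 mL (raw SD) or 20.0 mL (change-score SD).

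**The case against.** The best defence is that the power paragraph relates the two numbers itself: 100 is the sample for power, 120 is what must be recruited to get there, and the other sections simply quote the target. On that reading the scenarios with 80 or 90 completers are ones the plan was written to avoid. The plan also calls 20% conservative against past attrition below 10%, and at 10% loss 120 leaves 108 dyads with all three outcomes above 80%. The study is, moreover, titled a pilot-feasibility study.

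Much of this stands. The shortfall from 100 to 96 is minor, and the 7 to 8 point loss arises only if 100 are actually enrolled. Measured against the plan's own basis of 100 completers, enrolling 100 with 10% loss costs 79.5 − 75.1 = 4.4 points for WLZ; the larger figure compares with enrolling 120.

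It does not remove the fault. The aims use 100 for enrolment into the trial, not for completers. Even if 100 did mean completers, 120 does not yield 100 at the stated 20%. The favourable case at 10% loss holds only if 120 enter. And although this is a pilot, the plan makes explicit 80% power claims, which should match the number enrolled.

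**Conclusion.** The concern holds, and the text is wrong as written. At the plan's own 20% dropout, 120 recruited gives 96 completers, which costs under 2 points of power. The unreconciled 100 and 120 matter more: enrolling 100 would cost about 8 points for WLZ and intake at 20% loss and about 7 points at 10% loss, leaving both below 80% in either case. NCAFS power at the stated 1.32 points is not threatened. The power figures assume two-sided testing, 1:1 allocation and that the 120 recruited are the dyads randomised; the last fits an allowance for 12-week dropout but is not stated. The 96 and the conflict in the text need none of the power assumptions. This should be fixed, but it does not undermine the design.

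**What to change.** Use one target in the Statement of Purpose, in Subjects and Recruitment and in Power calculations, and label each number as randomised or completing. State the sidedness and the allocation ratio.

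**Option A (preferred).** In Power calculations write: *120 dyads will be randomised; with 20% attrition 96 are expected to complete, giving 80% power (two-sided α = .05, 1:1 allocation) for a difference of 0.61 in WLZ change and 19.5 mL in intake (SD 33.7 mL).* If the intake SD is meant for change scores, write 20.0 mL with SD 34.5 mL and say so.

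**Option B.** Keep the stated differences and replace the 20% estimate with: *120 dyads allow for 16.7% attrition, leaving 100.* The 20% figure must then be removed, or the paragraph contradicts itself. The 16.7% is still above the attrition previously seen.

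Under either option, change the number enrolled in the Statement of Purpose to 120. In Subjects and Recruitment, say that 120 will be randomised with 96 (A) or 100 (B) expected to complete. Keeping both 20% and 100 completers would instead require 125, five dyads more than planned.

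Deal with the 1.32-point NCAFS figure separately: the stated inputs give about 1.11 at 100 completers and 1.13 at 96. Until that is done, it should not be presented as resting on the same basis.

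**Cost.** The change is to wording, submitted as a modification request to the IRB, with no dyads beyond the 120 already in the power paragraph. If the study has in practice been set up for 100, moving to 120 means 20 more dyads, or 20 × $100 = $2,000 in participant compensation, plus their bottles and visits. Option A moves the detectable differences from 0.59 to 0.61 WLZ and from 19.1 to 19.5 mL (raw SD); Option B leaves them unchanged.
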